9.3.10 Disease Assessment

Patients will be assessed for disease response according to the European Group for Blood and Marrow Transplant criteria, modified and updated by the IMWG criteria (Appendix F).

For Parts 1 and 2, response assessments will be made on the basis of local laboratory data. For Part 3, response assessments will be made on the basis of central laboratory data.

Assessments should occur every cycle during treatment and every 4 weeks during the PFS/survival follow up period until disease progression (see SOEs). If the start of a cycle is delayed, serum M-protein and serum FLCs are to be collected for central laboratory analysis if not previously sent within the preceding 10 days. If a patient has collected a 24-hour urine sample and brought it to a visit, the sample should be sent for central laboratory analysis of urine M-protein even if not on Day 1 of a cycle.

Serum and urine response assessments will be performed as indicated in the SOEs (Appendix A). Imaging tests for qualifying patients (see Sections 9.3.10.1 and 9.3.10.2) are to be performed every other cycle beginning with Cycle 3 only for patients with extramedullary disease at screening or when there is a clinical suspicion of extramedullary progression. In extenuating circumstances, such as during the COVID-19 public health emergency, patients may use an alternative site for imaging with prior notification to the sponsor or designee.

CR should be confirmed follow up assessments (by local laboratories for Parts 1 and 2 and by central laboratories for Part 3) of serum protein electrophoresis (SPEP), urine protein electrophoresis (UPEP), immunofixation of blood and urine, and serum FLCs as outlined in the SOEs (Appendix A). One bone marrow assessment (locally evaluated for Parts 1, 2 and 3) is required to document CR; no second bone marrow confirmation is needed.

Please note that to determine a response of sCR, bone marrow immunohistochemistry or immunofluorescence for the κ : λ ratio, as well as serum FLC assay, should be performed for all patients suspected to be in CR to meet this response category's requirements.

For Parts 1 and 2, PD may be confirmed per standard clinical practice at the site. Local laboratories may be used to confirm PD. For Part 3, PD must be confirmed based on central laboratories.

The following disease assessments will be performed as indicated in the SOEs (Appendix A).

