13.3 Determination of Sample Size

Part 1 of the study will follow a standard 3 + 3 dose escalation design. Under this design, the probability of dose escalation according to the true DLT rate is as follows:

True DLT rate	5%	10%	20%	30%	40%	50%	60%	70%
Probability of escalating	97%	91%	71%	49%	31%	17%	8%	3%

DLT: dose-limiting toxicity.

The probability of not observing a DLT in a sample size of 6 patients according to the true DLT rate is as follows:

True DLT rate	5%	10%	20%	30%	40%	50%	60%	70%
Probability of no toxicity	74%	53%	26%	12%	4.7%	1.6%	0.4%	<0.1%

DLT: dose-limiting toxicity.

Patients will be considered evaluable in Part 1 for MTD/OBD assessment provided they have not missed any of their infusions of modakafusp alfa in Cycle 1 and have not had a DLT. Patients who are not considered evaluable as defined above will be replaced.

Part 2 Expansion

The study will enroll up to 25 patients in each arm to further characterize safety of the OBD/MTD and obtain preliminary clinical efficacy data. An OBD/MTD dose will be considered clinically relevant if at least 11 out of 25 response evaluable patients have a confirmed PR or better. With a vague beta prior with shape parameters 0.428 and 1 for ORR (ie, mean of 30%), 11 responders out of 25 gives a greater than 90% posterior probability of true ORR being greater than 30%. The design has reasonable operating characteristics. With a true ORR of 30%, the probability of declaring success is 7%. In contrast, with a true ORR of 50%, the probability of declaring success is 70%.

Part 3 Extension

The primary objective of Part 3 of the study is to determine the confirmed ORR, including PR, VGPR, CR, and sCR assessed according to the IMWG criteria (Appendix F) to modakafusp alfa in patients with MM previously treated with ≥3 lines and with evidence of disease progression who are refractory to, or intolerant of, a PI, an IMiD, and an anti-CD38 mAb (triple refractory). The sample size was determined to claim that the true ORR is greater than the threshold response rate of 20% within each treatment arm. A total sample size of approximately 236 enrolled patients (118 patients per arm) will allow the study to have over 90% power to rule out an uninteresting response rate of 20% if the true rate is 35% with a 1-sided alpha of 0.025.

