- h. Urinalysis (dipstick) will include bilirubin, glucose, ketones, leukocytes, nitrite, occult blood, pH, protein, specific gravity, turbidity and color, and urobilinogen. Microscopic if clinically indicated only: bacteria, RBCs, WBCs, casts, and crystals.
- Pregnancy test (refer to Section 9.3.9.2). A urine or serum pregnancy test is required at EOT in women of childbearing potential. If menstrual period is delayed, absence of pregnancy in women of childbearing potential must be confirmed by serum pregnancy test.
- Urine M-protein 24-hour urine sample required while on treatment and during follow-up only if urine M-protein is measurable at baseline (urine M-protein \geq 200 mg/24 hours).
- Immunofixation of serum and/or urine may be omitted at screening if a previous local laboratory report for the serum and/or urine protein electrophoresis states that the observed monoclonal spike is consistent with one previously characterized by immunofixation and specifies the heavy chain and light chain previously identified. Immunofixation in serum and urine is required for patients evaluated for CR.
- A blood sample for quantification of Ig (IgM, IgG, and IgA) will be obtained. For the rare patient with known IgD or IgE MM, the quantitative test for that antibody will be followed at the same time points throughout the treatment period and PFS follow-up period as quantitative IgS (in addition to quantitative IgM, IgG, and IgA).
- m. See Appendix B for details.
- ^{n.} Immunoprofiling consists of flow cytometric analysis of T, B, and NK lymphocyte subsets and will be analyzed centrally.
- ^{o.} Blood samples for immunogenicity (ADA and NAb) testing will be collected, if possible, at the EOT follow-up visit.
- Only repeat tests in parentheses for patients terminating treatment due to PD, if they were not performed before for PD determination at the last visit, and for patients discontinuing due to treatment completion or CR if not performed before for CR confirmation.
- Patients who discontinue for reasons other than PD will continue PFS follow-up every 4 weeks from the EOT visit until the occurrence of PD, death, the start of subsequent systemic antineoplastic therapy, study termination, or until 6 months after the discontinuation of study treatment, whichever occurs first.

- End-of-treatment laboratory assessments are to be performed prior to the patient starting a new treatment or a maximum of 30 days following the last dose.

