Study Period						Treatr	nent Phase							FU
Cycle Day	C3 D1	C4 D1	C5 D1	C5 D2	C6 D1	C7 D1	C8D1 to C10D1	C11 D1	C11 D2	C12 D1	C13 D1+	EOT 30 (+10) days after last dose or the start of subsequent		OS Every 12 weeks
Window Allowed	±2 d	±2 d	±2 d	±0 d	±2 d	±4 d	±4 d	±4 d	±0 d	±4 d	±4 d	systemic anticancer therapy whichever occurs first aa	weeks bb	±1week ^{cc}
Serum FLC assay (central analysis) m, q	X	X	X		X	X	X	X		X	X	(X) ^z	X	
Immunofixation - serum & urine ^{r (} central analysis)	X	X	X		X	X	X	X		X	X	(X) ^z	X	
Serum sample for interference testing ^{kk} (central analysis)	(X)	(X)	(X)		(X)	(X)						(X) ^z	(X)	
Quantification of Ig s (central analysis)	X	X	X		X	X	X	X		X	X	(X) ^z	X	
BMA for disease assessment t, ii (local analysis)		le to be time o				ected CI	R to confir	m respo	nse (CR	/sCR); o	optional			
BMA for MRD (central analysis) ff		ole to be nts in C		ected a	it suspe	ected CI	R and ever	y 6 mon	ths there	eafter fo	r			
Investigator assessment of disease/response status	X	X	X		X	X	X	X	X	X	X	X	X	
Subsequent therapies/disease status														X
Biologic Assessments (c	entral	analys	is)											
Serum sample for modakafusp alfa PK ^u	X	X	X	X °	X	X	X	X	X °	X	X	X		
Fresh BMA ii	Optio	nal san	nple to	be c	ollected	d at prog	gression af	ter resp	onse. hh					

Appendix A Table 1	13	Pa	art 3	Exte	ension	Sche	dule of H	Events	, Cont	inued:	Cycle	3 through EOT and	FU	
Study Period						Treat	ment Phase							FU
Cycle Day	C3 D1	C4 D1	C5 D1	C5 D2	C6 D1	C7 D1	C8D1 to C10D1	C11 D1	C11 D2	C12 D1	C13 D1+	EOT 30 (+10) days after last dose		OS Every 12 weeks
Window Allowed	±2 d	±2 d	±2 d	±0 d	±2 d	±4 d	±4 d	±4 d	±0 d	±4 d	±4 d	or the start of subsequent systemic anticancer therapy, whichever occurs first ^{aa}	weeks bb	±1week ^{cc}
Serum sample for circulating biomarkers ^f			X dd	X °				X dd	Χ°			X		
Serum sample for immunogenicity (ADA/NAb) ^{f, y}	X	X	X		X	X	X	X		X	X	X	X	
Blood sample for RNA			X dd	X °				X dd	Χ°					
Blood sample for receptor sequencing w, hh	X		X			X		X						
Plasma sample for ctDNA w, hh			X					X						
PRO and Healthcare Resource Utilization Assessments														
EORTC QLQ-MY20 ee		A	At Cyc	cle 2 a	ınd bey	ond, PI	ROs data aı	e collec	ted on I	Day 8		X		
EQ-5D-5L ee		Α	t Cyc	le 2 a	nd beyo	ond, PR	Os data ar	e collect	ted on D	ay 8.		X		
Healthcare resource utilization data ee					Γ	Day 1 of	f every cyc	le.				X		

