- A blood sample for quantification of Ig (IgM, IgG, and IgA) will be obtained. For the rare patient with known IgD or IgE MM, the quantitative test for that antibody will be followed at the same time points throughout the treatment period and PFS follow-up period as quantitative IgS (in addition to quantitative IgM, IgG, and IgA) (see Section 9.3.10.3). To be repeated at baseline (C1D1) if screening sample was taken more than 7 days before C1D1.
- For local analysis of disease assessment and cytogenetics at screening, a standard BMA drawn before consent is acceptable provided this is collected within 5 weeks of the first dose. All patients should also have a sample from screening sent for central cytogenetic analysis ("BMA for cytogenetics").
- u. Blood samples for PK will be collected at time points specified in Appendix C, Tables 9 and 10.
- v. All patients should have a fresh BMA sample from screening sent for central cytogenetic analysis.
- w. Predose.
- x. Coagulation panel (prothrombin time/international normalized ratio, activated partial thromboplastin time, fibrinogen, D-Dimer) to be performed if clinically

significant bleeding occurs.

- Blood samples for immunogenicity (ADA/NAb) testing will be collected before the dose on indicated visits during treatment and, if possible, at the EOT visit. In case of an infusion reaction, blood draws should be performed for central evaluation of immunogenicity (see Section 8.7.1.1). On days when dosing is not required, samples may be collected at any point during the clinic visit.
- ^{z.} Only repeat tests in parentheses for patients terminating treatment due to PD if they were not performed before for PD determination at the last visit, and for patients in CR if not performed before for CR confirmation.
- End-of-treatment laboratory assessments are to be performed prior to the patient starting a new treatment or a maximum of 30 days following the last dose.
- Patients will have PFS follow-up every 4 weeks from the EOT visit until the occurrence of PD, death, the start of subsequent systemic antineoplastic therapy, study termination, or until 6 months after the discontinuation of study treatment, whichever occurs first.
- cc. OS follow-up continues every 12 weeks until death, study termination, or patient withdrawal.
- dd. Predose and at 4 hours (\pm 60 minutes) after the end of infusion.

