Appendix H Operating Characteristics of the Futility Stopping Rules

The stopping rules used for the treatment arms of 240 mg and 120 mg at each interim futility analysis were chosen to have reasonable operating characteristics as displayed in this section (Appendix H Table 1 and Appendix H Table 2).

Based on the proposed 2 interim futility analyses criteria (Section 13.2.2.1 Part 3 Futility Stopping Rules), the design operating characteristics were calculated for each of the treatment arms under different true ORR scenarios.

Appendix H Table 1 displays the corresponding operating characteristics for the treatment arm of 240 mg, including cumulative probability of terminating the arm early at each interim analysis, average number of patients enrolled and followed up for 3 months, average number of responders observed, and probability of success (PoS) at primary analysis. As there is no plan for efficacy claim based on any of the interim analyses, the only time to claim a positive efficacy conclusion (success for each arm) will be at the primary analysis. The success criterion will be a minimal of 33 responders among 118 treated patients, achieving the goal of lower limit of 95% CI above 20% uninteresting rate.

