In addition, time to the best response (the time from the first dose to the date of the first documentation of the best confirmed response [PR or better]) will be analyzed by using the same approach.

Overall Survival (OS)

Overall survival is defined as the time from the date of first dose to the date of death from any cause. Patients without documentation of death at the time of analysis will be censored at the date last known to be alive.

OS (months) = (date of death or censor – date of first dose + 1)/30.4375

The analysis of OS will be based on safety analysis set. The Kaplan-Meier method will be used to analyze the distribution of OS. Kaplan-Meier survival curves, the 25th, 50th (median), and 75th percentiles, along with the associated 2-sided 95% CIs based on Brookmeyer and Crowley method, and Kaplan-Meier estimates with 95% CIs at 6 and 12 months (or later time points if

data permits) will be presented. The number of patients with events and the number of patients censored will be summarized.

Best Overall Response

Best overall response is defined as the best response recorded after the first dose of study drug until subsequent anti-cancer therapy.

Confirmation of Response: All response categories except SD (sCR, CR, VGPR, PR, PD) require 2 consecutive adequate assessments made at any time before the initiation of subsequent anti-cancer therapy. There is no requirement on the time interval between the two visits.

Consecutive visits are needed for response confirmation, except if there is one or two “not evaluable” (NE) or “not done” (ND) assessments in between.

Either one or two consecutive occurrences of “ND” or “NE” between responses can be skipped when confirming a response such as:

PR -> NE -> PR: PR is considered to be confirmed in this case.

CR -> ND -> CR: CR is considered to be confirmed in this case.

Confirmation of PD:

1. If only one PD is recorded as the last available assessment prior to the subsequent anti-cancer therapy, it can be counted as a confirmed PD. It will be considered as an event for DOR, TTP, PFS analyses.

BL → SD → PD → Subsequent anti-cancer therapy/End – It is a confirmed PD

2. If only one PD value is recorded in the middle of responses better than PD as below, it will not be counted as a confirmed PD. It will not be considered as an event for DOR, TTP, PFS analyses.

BL → SD → PD → SD → SD → Subsequent anti-cancer therapy/End – It is not a confirmed PD.

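### Part 3 footnote z omits the end-of-treatment response tests for patients with a first, unconfirmed PR or VGPR; those with no later PFS visit lose their last chance of confirmation and count as non-responders.

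*Protocol*

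**What the plan says.** **The EOT tests.** In the EOT column of protocol Appendix A Table 13, serum M-protein, 24-hour urine M-protein, serum FLC, immunofixation, interference testing and quantitative Ig are all in parentheses and carry footnote z, which reads: "Only repeat tests in parentheses for patients terminating treatment due to PD if they were not performed before for PD determination at the last visit". The footnote adds only patients in CR whose CR has not yet been confirmed.

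**The EOT rating.** The row "Investigator assessment of disease/response status" has an unconditional X at EOT. Protocol 9.3.10 states: "For Part 3, response assessments will be made on the basis of central laboratory data". Footnote m of the same table requires every response to be confirmed by the central laboratory.

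**Confirmation.** SAP 7.8.2.1 bases Part 3 ORR on confirmed responses and refers to the best-overall-response rules, under which all categories except SD "require 2 consecutive adequate assessments made at any time before the initiation of subsequent anti-cancer therapy". Assessments after new systemic therapy are not used.

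**Target.** The protocol's sample-size section (13.3) plans 118 patients per arm for over 90% power against a 20% rate "if the true rate is 35% with a 1-sided alpha of 0.025". Appendix H gives the rule: "The success criterion will be a minimal of 33 responders among 118 treated patients".

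**The concern.** The schedule asks for a response rating at EOT in everyone, but provides the central data for it only in patients stopping for PD or in CR. The primary endpoint needs two assessments, so the omission matters most for a patient with just one.

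Take a patient with a first PR at C2D1 who is dosed and then has a bleeding event or infusion reaction that ends treatment mid-cycle (Tables 8.e and 8.h foresee such stops). C3D1, where the confirming sample would have been drawn, never takes place. The EOT visit draws chemistry and hematology but no response tests. If new systemic therapy follows at once, no further assessment counts, and a response that may have been real enters the primary analysis as a non-response.

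**Working it through.** **Step 1. Who is left out at EOT.** Footnote z covers patients stopping for PD and patients in CR. A patient in PR or VGPR who stops for another reason is not covered. For ORR only the first PR or better is exposed: once PR is confirmed, a missing EOT test cannot remove the patient from the numerator.

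**Step 2. When the next sample is due.** EOT is 30 (+10) days after the last dose, or the start of new systemic therapy if that is earlier. PFS visits follow every 4±1 weeks from EOT, with M-protein, urine, FLC, immunofixation and Ig marked by a plain X.

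- Earliest first PFS visit: 30 + 21 = 51 days after the last dose.
- Latest: 40 + 35 = 75 days.
- PFS follow-up ends at PD, death, new systemic therapy, study termination or 6 months after treatment stops.

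**Step 3. What the SAP accepts.** SAP 5.3.4 and 7.8.2.1 include assessments made after treatment discontinuation. SAP 7.8.1 sets no interval between the two assessments and lets one or two not-done or not-evaluable visits be skipped. PR at C2D1, nothing at EOT, PR at the first PFS visit is therefore a confirmed PR.

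**Step 4. Who remains.** Confirmation is lost through this gap only if the patient (a) has a single assessment of PR or better, (b) stops for a reason other than PD with no confirming sample in a delayed cycle, and (c) starts new systemic therapy, dies or withdraws before the first PFS visit.

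**Step 5. Reproduce the plan's figures.** Exact binomial, n = 118, success at 33 or more:

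- P(X ≥ 33 | 0.20) = 0.0235, below 0.025.
- Exact 95% lower limit: 20.1% at 33/118 and 19.3% at 32/118, so 33 is the right cut-off.
- P(X ≥ 33 | 0.35) = 95.7%, consistent with over 90%.
- With both futility looks, the probability of success at 35% is 89.4% (240 mg) and 93.2% (120 mg); Appendix H states 89% and 93%.

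**Step 6. Effect of lost confirmations.** Each loss lowers observed ORR by 1/118 = 0.85 points. If k true responders per arm are lost, 33 + k are needed, so the fixed-sample chance is P(X ≥ 33 + k). The values of k are assumptions.

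| k lost per arm | True ORR 35% | True ORR 30% |
|---|---|---|
| 0 | 95.7% | 71.7% |
| 1 | 93.6% | 64.4% |
| 2 | 90.7% | 56.7% |
| 3 | 86.9% | 48.7% |
| 4 | 82.3% | 40.8% |

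For scale, 0.35 × 118 = 41.3 responders are expected per arm, so two lost is about 5% of them and four about 10%.

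**Step 7. With the futility looks.** If a share f of responders is lost at every look, the effective ORR is 0.35 × (1 − f). At f = 2% it is 34.3%, with probability of success 87.3% (240 mg) and 91.3% (120 mg). At f = 5% it is 33.25%, with 83.3% and 87.5%.

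**The case against.** The strongest reply is that follow-up already does the job. The PFS tests are unconditional, 9.3.10 requires assessment every 4 weeks until progression, and the SAP accepts those results and passes over a missed EOT. This stands. A reader might infer that a first PR in any patient who stops for toxicity may never be confirmed; the documents do not support that for the group as a whole. Nor is EOT the last assessment for everyone who later changes treatment: patients who start new therapy after the first PFS visit have been sampled again by then.

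Other coverage also narrows the gap. Many Part 3 toxicity rules hold the next infusion first, and a delayed cycle triggers central serum M-protein and FLC unless sent within the preceding 10 days (9.3.10). That does not help a patient stopped mid-cycle without a hold, and it does not require urine, which the PR criteria in Appendix F use. Footnote m is a general duty to confirm centrally, but it does not schedule an EOT sample that the table makes conditional.

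It would be too strong to say that the EOT rating is made with no data, since earlier central results and available imaging exist. What is missing is a current central sample.

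The objection to the magnitude also stands in part. No rate is given, so the number lost could be zero. The 35% planning rate may already be net of such losses, since the endpoint is confirmed ORR. A reader might also infer that the loss biases the choice between doses. That needs different rates of toxicity stops in the two arms, which the documents do not give; Part 3 makes no formal comparison between arms, and the dose choice rests on the totality of data.

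**Conclusion.** There is a real but narrow scheduling gap. Footnote z does not fit the unconditional EOT rating or the reliance on central data. It can cost a confirmation only in patients with a single PR or VGPR who start new systemic therapy, die or withdraw before the first PFS visit, 51 to 75 days after the last dose when EOT follows the 30 (+10) day rule. They count as non-responders in the confirmed IRC-assessed ORR.

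Their number cannot be derived from the documents. Each costs 0.85 ORR points. The fixed-sample power claim survives one or two losses per arm (93.6%, 90.7%) and would fail at three (86.9%), if the 35% is counted before such losses. The documents therefore do not show that the trial is underpowered because of this. The case for change is that an avoidable loss from the primary endpoint can be removed at little cost.

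**What to change.** Amend footnote z in Appendix A Table 13. For every patient without documented PD, draw serum M-protein, FLC, immunofixation and quantitative Ig at EOT, before any new systemic therapy, with 24-hour urine where it can be collected in time. Exempt samples already sent centrally within the preceding 10 days, the interval 9.3.10 uses for delayed cycles. The minimum version covers only patients with an unconfirmed response at EOT. Keep the present condition for patients stopping for PD.

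The cost is a footnote edit and one extra central-laboratory sample set per affected patient, at a visit where blood is already drawn for chemistry and hematology.

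Table 11 (Parts 1 and 2) has a similar restriction: "Only repeat tests in parentheses for patients terminating treatment due to PD, if they were not performed before for PD determination at the last visit". It is not identical, since it also covers patients who complete treatment. It could be aligned for consistency, but it does not bear on the Part 3 primary endpoint.
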